7.2.3 Radiation dosimetry

In order to examine the effect of mean equivalent dose in 2Gy fractions (EDQ2) to various brain structures and associations with impairment status, univariate logistic regression analyses will be undertaken. Wald tests will be used to test the statistical significance of each model, using two-tailed tests. P-values <0.05 will be considered significant.

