3.1 Trial objectives

The aim of this trial is to study the long-term impact of multimodal treatment (chemotherapy, radiotherapy and surgery) in adult brain and base of skull tumours on neurocognitive functioning using neuropsychological testing combined with advanced MR imaging techniques in a multicenter observational cohort study. We differentiate two main objectives.

The first objective is to build an NTCP model for neurocognitive decline after RT (for each cognitive domain separately), linking dose-volume parameters to structures within the brain susceptible to neurological damage and neurocognitive decline after radiotherapy. These NTCP models will be used to make predictions on neurocognitive decline in future primary brain tumour patients receiving cranial RT. It will provide us with a much needed, evidence-based tool to select the optimal treatment modality for each individual patient and enables us to tailor cranial irradiation towards neurocognition-sparing treatment in the future.

The second objective is to evaluate dose-dependent neurocognitive decline. In particular, we will investigate:

- Prevalence and severity of neurocognitive decline after RT for all cognitive domains
- Brain structures or functional brain connections important in neurocognitive functioning (based on dedicated MRI).
- Dose-dependencies of specific neurocognitive skills after RT in adult brain tumour patients
- Correlations between RT dosimetry and early brain changes (MRI)

With this prospective observational trial, we aim to map the neurocognitive side effects of the irradiation treatment in cranially irradiated patients and the clinical and dosimetrical factors that play a role. Based on these findings, we plan to set up future prospective trials to validate these findings.

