7.2.1 Neuropsychological data

The following research questions are addressed by using multiple statistical tests.

- 1. How severe is the neurocognitive decline after treatment and how does it change over time?
- 2. Which neurocognitive domains are affected in which patients?

The first question is addressed by investigating the neurocognitive performance of primary brain and base of skull tumour patients. The performance on neurocognitive measures of the patients will be assessed at 3 timepoints over time. The raw test-scores are converted to normalized zscores based on normative data for each cognitive test. For each cognitive test, cognitive impairment is defined as a z-score \leq 1.5, and patients will be dichotomized according to their impairment status (impaired versus unimpaired). The frequency of impairment will be reported as descriptive information.

We will assess the evolution in the z-scores with a mixed repeated measures model to test changes throughout time. However, if the data are not normally distributed, the Friedman test will be used as alternative approach. The effects of the patient- and treatment-related predictors on the neuropsychological and questionnaire scores will be investigated using general linear models (predictors= tumour location, radiation dose, covariates= gender, age at treatment, time since treatment and socio-economic status) at each timepoint. Bonferroni correction will be applied as

method for statistical correction of multiple tests, for each test outcome (n=5 outcomes; memory, executive functioning, attention, visuomotor function, working memory) that is predicted.

Effect sizes of the tests will be reported. Partial eta squared (hp2) will be computed to estimate effect sizes (weak effect: $np^2 \approx 0.03$; moderate: $np^2 \approx 0.06$; large: $np^2 \geq 0.14$) for linear relationships between predictor and each outcome (e.g. age, time since treatment). Cohen's d will be used to estimate effect sizes for subgroup differences (small effect: 0.2 < d < 0.3; medium: 0.3 < d < 0.8; large: d > 0.8).

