7.2.2 Imaging

State of the art image analysis approaches are applied to process and analyze the acquired brain images and to document individual changes in structural white matter or resting state brain activity. Structural MRI data will be analyzed via voxel based morphometry (VBM) in Statistical Parametric Mapping (SPM). Multiple validated toolboxes will be used (e.g. FreeSurfer, ANTs, CAT12). To correct for distortions caused by the brain tumour itself, Virtual Brain Grafting will be used⁴⁵. DWI images will be processed and analyzed using MRtrix 3.0. Seed-based analysis and independent component analysis (ICA) will be applied to analyze the resting state fMRI data. The association between the obtained MR parameters and the performance on neurocognitive tests will be investigated using (voxel- and region of interest-based) correlation analyses. The independent effects of the predictors (radiation dose, gender, age at treatment, duration of treatment and socioeconomic status) on these neuropsychological test scores and imaging feature values will be analyzed with a (voxel-based) general linear model. For the MR analyses, repeated measures ANOVA will be conducted voxel-based to analyze the within-subject variability in tissue probability maps throughout time (e.g. grey matter or white matter volume, grey matter density, white matter microstructure). The significance threshold will be set at p < 0.05 false discovery rate (FDR) corrected for multiple comparisons.

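### Section 7.2.3 declares structure-dose effects significant at an uncorrected p<0.05 from unadjusted models with no baseline score, although 7.2.1 and 7.2.2 correct for multiplicity

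*Protocol*

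**What the plan says.** The exposure in 7.2.3 is the "mean equivalent dose in 2Gy fractions (EDQ2) to various brain structures". To study its association with impairment status, "univariate logistic regression analyses will be undertaken". The test rule is explicit: "Wald tests will be used to test the statistical significance of each model, using two-tailed tests", and "P-values <0.05 will be considered significant". The section names no covariate, no baseline term and no multiplicity correction.

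Impairment status is defined in 7.2.1: each test score is converted to a z-score from normative data, a cut-off is applied, and "patients will be dichotomized according to their impairment status (impaired versus unimpaired". The definition concerns the level of the score at a visit, not its change since baseline.

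The neighbouring sections work differently. Section 7.2.1 fits general linear models to the scores, with tumour location and radiation dose as predictors and gender, age, time since treatment and socio-economic status as covariates, and applies Bonferroni over five outcomes. Section 7.2.2 sets its threshold as "false discovery rate (FDR) corrected for multiple comparisons".

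The dose question is a stated aim. Section 3.1 lists "Dose-dependencies of specific neurocognitive skills after RT in adult brain tumour patients" among the items to be investigated, and section 3.3 makes the association between neurocognitive functioning and dosimetry a secondary endpoint.

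**The concern.** Three features of 7.2.3 act together.

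- **Error rate.** Every structure-by-outcome pair has its own 5% chance of a false claim, with nothing to limit the total.
- **Confounding.** Tumour site largely determines which structures receive a high dose, and it can itself impair function. Because status is a level and not a change, a patient already impaired before radiotherapy counts as an event. An unadjusted model cannot separate that from a dose effect.
- **Two decision rules for one question.** Dose and cognition are tested with adjustment and correction in 7.2.1, and without either in 7.2.3. A dose effect could be significant under one rule and not the other, and the protocol does not say which governs.

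Section 3.1 intends the results to steer irradiation towards sparing cognition. A structure wrongly labelled dose-sensitive would misdirect that work.

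**Working it through.** **The plan's own figures.** The protocol gives no power or error figure for the 7.2.3 tests. The figures in 7.1 concern the mean change over 12 months. They reproduce with a two-sided paired t-test at 0.05, noncentrality d√n:

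- d = 0.368, n = 60: power 0.8006 (stated 0.800).
- d = 0.368, n = 120: noncentrality 0.368 × √120 = 4.03, power 0.979 (stated 0.979).
- d = 1.271, n = 8: power 0.867 (stated 0.868).

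They are sound for that purpose but say nothing about testing many structure doses.

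**Inputs for the error rate.** The level is 0.05 per test (7.2.3). There are five domains (7.2.1, 7.2.4), or 11 test outcomes if the table in 5.2 is counted line by line. The number of structures is not given; 10 to 20 is my assumption.

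**Expected false positives if dose has no effect** = number of tests × 0.05. Correlation between tests does not alter this count.

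- 5 domains × 10 structures = 50 tests: 50 × 0.05 = 2.5.
- 5 domains × 20 structures = 100 tests: 100 × 0.05 = 5.
- 11 outcomes × 10 structures = 110 tests: 110 × 0.05 = 5.5.
- 11 outcomes × 20 structures = 220 tests: 220 × 0.05 = 11.

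**Chance of at least one false positive.** For independent tests this is 1 − 0.95^m. Structure doses and cognitive scores are correlated, so the independent column is an upper figure. The other columns come from simulating equally correlated normal test statistics.

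| Tests | Independent | Correlation 0.5 | Correlation 0.8 |
|---|---|---|---|
| 5 (one structure) | 22.6% | 18% | 13% |
| 25 (five structures) | 72.3% | 47% | 24% |
| 50 (ten structures) | 92.3% | 62% | 30% |
| 100 (twenty structures) | 99.4% | 78% | 36% |

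All entries exceed 5%, including a single structure tested over five domains.

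**What the other sections' rules would imply.** Bonferroni over five outcomes, as in 7.2.1, gives 0.05/5 = 0.01 per test. Counting structures as well gives 0.05/50 = 0.001 or 0.05/100 = 0.0005.

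**Confounding.** The counts above cover chance alone. Suppose dose does nothing, but a tumour next to a structure both raises that structure's dose and has already lowered the related score. The univariate odds ratio then departs from 1, and its chance of reaching p<0.05 exceeds 5% and grows with sample size. No multiplicity correction removes this; only adjustment for baseline score and location addresses it.

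**Dichotomising.** For a normal outcome cut so that a fraction p are events, efficiency relative to the continuous score is φ(z_p)²/[p(1−p)]. At the event rates in 7.1:

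- p = 0.2: 0.280²/0.16 = 0.49.
- p = 0.5: 0.399²/0.25 = 0.64.

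The 7.2.3 tests thus lose 36% to 51% of the information in the score.

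**The case against.** The strongest reply is that 7.2.3 is not the only place where dose is studied. Section 7.2.1 already has a general linear model on continuous scores with dose, location and covariates, corrected over five outcomes. Section 7.2.2 estimates the independent effect of dose on test scores under a false discovery rate threshold. Section 7.2.4 adds atlas-structure doses to clinical models whose candidates include location, age and education, with cross-validation and optimism correction. This stands, and it limits the point. A reader might infer that the trial examines dose only without adjustment; the protocol does not support that. The adjusted analyses do not repair 7.2.3, however. The dose term in 7.2.1 is not stated to be per structure, 7.2.2 does not list tumour location, and the 7.2.1 covariates omit the baseline score.

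Second, 7.2.4 also uses an uncorrected p = 0.05, so 7.2.3 is not alone in that. But there the threshold selects variables within an internally validated prediction model and is not a claim about a structure. Nor does the text make p<0.05 in 7.2.3 a condition for entry to the NTCP model: 7.2.4 ranks by area under the curve.

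Third, an NTCP model needs a binary outcome. That is true for 7.2.4, and it is a reason to keep the logistic odds ratios as description. It does not require the association tests to be run on the dichotomy. The information loss applies to the 7.2.3 tests only, since 7.2.1 keeps the continuous scores; a loss of that size for the whole study cannot be inferred.

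Fourth, the protocol calls the study exploratory and foresees later validation. That argues for false discovery rate control over strict family-wise control. It does not explain correcting in 7.2.1 and 7.2.2 but not here.

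**Conclusion.** The point holds for the significance claims of 7.2.3 and no further. As written, that section leaves its error rate uncontrolled and lets pre-radiotherapy impairment and tumour location pass as dose effects. With an assumed 10 to 20 structures and five domains, 2.5 to 5 false positives are expected if dose has no effect. The chance of at least one lies between 30% and 99%, depending on the number of tests and their correlation. The size rests on the structure count, which the protocol does not give. That the error rate exceeds 5% does not depend on that count, since five domains and one structure already give 13% to 23%. The size of the confounding cannot be computed from the document. It would go too far to say that structures are certain to be mislabelled, or that the adjusted dose analyses elsewhere are affected.

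**What to change.** For the structure-dose tests in 7.2.3:

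1. Use the 12-month z-score as outcome in a linear model on the structure's mean EQD2, adjusted for baseline z-score, age, education and tumour location. Section 7.2.1 defines z-scores per test, so either run the model per test or state how a domain composite is formed.
2. Control the false discovery rate at 5% over all structure-by-outcome tests, and list the structures in advance so that the family is fixed.
3. Keep the univariate logistic odds ratios with confidence intervals as description, without significance claims.

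No new data or visits are needed: baseline testing, education and tumour location are already collected. The costs are some analysis work, fewer nominally significant structures, and wider intervals where structure dose and tumour location are collinear. The last is a real loss of precision at n = 120, but it shows how far these data can separate dose from site.

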7.2.4 NTCP modeling

Two NTCP modelling efforts will be conducted for each cognitive outcome domain (attention, memory, executive functioning, working memory, Information/visuomotor processing speed). In the first effort, dose metrics of anatomical structures derived from a brain atlas will be used together with clinical patient factors to develop a prediction model of neurocognitive decline. First, univariable logistic regression analysis will be performed to select clinical parameters associated with cognitive outcome. These variables will be ranked based on their association (area under the curve (AUC) of the univariable logistic regression) with the endpoint. The best ranked variable will be selected first. Subsequently, each next variable will be excluded from the ranking if its Pearson's correlation is r > 0.8 with any previously selected variable. For the remaining variables, we will check whether non-linear transformations (log, square root, inverse transformations, etc.) improves the association. Considered clinical variables in model building are: gender, age at diagnosis, tumour location, treatment modality, pathology, education, time since treatment. The added value of dosimetry to the use of clinical information will be verified in three steps. Initially,

a multivariable prediction model (logistic regression model with LASSO regularization) will be built with only the clinical variables using a forward stepwise procedure with p = 0.05 (deviance criterion) as critical p-value to stay in the model. Afterwards, the clinical prediction model will be extended by a stepwise addition of dosimetric variables which are ranked in the univariable analysis. In this multivariable prediction model (LASSO), a maximum of 4 variables will be included in each model. Finally, we will test in all models whether proton beam therapy (PBT) itself has an additional independent impact on the outcome risk apart from the already selected dose metrics. If that is the case, this will be investigated further by linear energy transfer (LET) and relative biological effectiveness (RBE) weighted PBT dose maps instead of the standard (RBE=1.1) PBT dose maps. The discriminative ability of the prediction models will be quantified using the AUC and compared between nested models using the likelihood ratio test. To obtain stable prediction models, all modelling steps will be repeated in a 100 times repeated 5-fold cross-validation process. The most frequently obtained models will be selected. Final model coefficients will be determined by fitting these selected models on the complete development dataset. Correction for optimism will be performed using 500 bootstrap samples.

In a second effort, relevant 3D clusters of brain voxels resulting from the brain damage susceptibility heat maps will be included in the modelling. Dose to these brain areas will be used as alternative dosimetric input parameters and the resulting model's performance will be compared to that obtained in the first step. The final NTCP model parameters will be calculated for the whole dataset of patients and per institution in order to detect potential heterogeneity.

Internal validation of the model will be performed using bootstrapping. After external validation, the final NTCP models could possibly be included in decision support software. In case of conflicting neurotoxicity constraints, several 'optimal' solutions to the planning problem (prioritizing one or another brain region) might indeed be possible. This will facilitate plan comparisons and informed decisions on the optimal treatment plan in future patients.

8. Quality assurance

The Principal Investigator will be responsible to ensure the study is conducted in accordance with the protocol, Good Clinical Practice (GCP), applicable regulatory requirements, and that the data recorded is valid. To achieve this objective, the study will be continuously monitored and reviewed monthly by the study team.

Clinical site monitoring is conducted to ensure that the rights and well-being of human subjects are protected, that the reported trial data are accurate, complete, and verifiable, and that the conduct of the trial follows the currently approved protocol/amendment(s), with GCP, and with applicable regulatory requirement(s).

MR quality will be checked with initial phantom scans acquired at each site. The neuro-MR protocol will also be tested and optimized at each participating center.

9. Direct access to source data and documents

The investigators and the institutions will permit trial-related monitoring, audits, EC review, and regulatory inspections (where appropriate) by providing direct access to source data and other documents (ie patients' case sheets, MR reports, histology reports etc).

10. Ethics and regulatory approvals

The trial will be conducted in compliance with the principles of the Declaration of Helsinki (current version), the principles of GCP and in accordance with all applicable regulatory requirements. This protocol and related documents will be submitted for review to Ethics Committee for Clinical Trial Authorisation.

The Study can and will be conducted only on the basis of prior informed consent by the Subjects, or their legal representatives, to participate in the Study. The Participating Site shall obtain a signed informed consent form (ICF) for all patients prior to their enrollment and participation in the Study in compliance with all applicable laws, regulations and the approval of the Ethics Committees (UZ Leuven, UZ Gent and GZA). The Participating Site shall retain such ICFs in accordance with the requirements of all applicable regulatory agencies and laws.

The Investigator and the Participating Site shall treat all information and data relating to the Study disclosed to Participating Site and/or Investigator in this Study as confidential and shall not disclose such information to any third parties or use such information for any purpose other than the performance of the Study. The collection, processing and disclosure of personal data, such as patient health and medical information is subject to compliance with applicable personal data protection and the processing of personal data (Regulation (EU) 2016/679 also referred as the General Data Protection Regulation ("GDPR") and the Belgian Law of July 30 2018 on the protection of natural persons with regard to the processing of personal data).

11. Data Handling and Management

The collection of personal patient information will be limited to the amount necessary to achieve the aims of the research, so that no unneeded sensitive information is being collected. Only study personnel will collect data. Klinisch Werk Station (UZ Leuven) and EPD (GZA, UZ Gent) will be used to assemble the clinical data of the patients who are eligible and willing to participate. The dosimetric data (e.g. mean EDQ2 of delineated structures) will be extracted from the therapy planning system (ARIA and Raystation).

An excel file containing the data of all eligible patients will only be saved on the internal server of the local hospital (password protected). We will collect the following personal information: EAD number (patient verification number of KWS), date of birth, pathology and date of diagnosis. This dataset will be coded (pseudonymized) in a separate password-protected excel file. These coding documents, which associate patient ID numbers with their individual code will only be saved on the internal server of the local hospital (GZA, UZ Gent and UZ Leuven).

The pseudonymized data per patient (without patient identifiers) will be complemented with additional clinical information, stored and shared by the study team using the REDCap data

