7.1 Sample size

Study subjects will be recruited from the radiation-oncology center of three centers: UZ Leuven, UZ Gent and Iridium Kankernetwerk Antwerpen. From a pragmatic perspective, we estimate to recruit 12-15 patients yearly in each of the three centers, resulting in 120 patients in three years in total.

Cognitive impairment has been reported in primary brain tumour patients and is roughly estimated to be present in about half of patients³⁹⁻⁴⁰. Although limited (good quality) evidence exists for our

type of study, power calculations were performed based on the two most extreme studies (i.e. one showing minimal amount of cognitive impairment⁴¹ and one showing maximal amount of cognitive impairment⁴². In both studies cognitive performance is assessed at baseline and about 12 months after radiotherapy in primary brain tumours. In the study by Moretti et al⁴², we used the cognitive outcome results of patients 9-12 months after radiotherapy (45-60 Gy), since the studied population will receive radiotherapy doses within this range. For power calculations, we used the performance on the digit span forward (processing speed) since the prevalence of impairment on this test was low (<20%). Based on these studies, effect sizes of d= 0,368 and d= 1,271 were found with a power of 0,800 and 0,868 respectively. This power would be 0,979 and 1,000 in our specific explorative study, in case of 120 inclusions. In order to detect this difference after 12 months with a power of 0.800 and a two-sided significance level α =0,05, the total required sample size would thus range between 8-60 patients. Power calculations were performed using Gpower 3.1⁴³.

Sample size calculation for the prediction models was performed using a recently developed software package⁴⁴. Since the event rate of cognitive impairment is unclear, we performed power calculations for the lowest and highest event rate, i.e. 0,2-0,5 (see above). When considering 4 candidate predictors and rMSPE of 0,1, the required sample sizes ranges between 90 and 120 patients respectively. Therefore, including 120 patients will allow building a sufficiently complex prediction model combining four dosimetric and/or clinical features.

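### The transformation check in section 7.2.4 is judged by univariable AUC, which cannot distinguish log, square-root or inverse forms from the untransformed variable on merit

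*Protocol*

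**What the plan says.** Section 7.2.4 of the protocol starts each NTCP model with a univariable screen. The ranking rule is: "These variables will be ranked based on their association (area under the curve (AUC) of the univariable logistic regression) with the endpoint". Variables that correlate above 0.8 with one already chosen are dropped. For those that remain, "we will check whether non-linear transformations (log, square root, inverse transformations, etc.) improves the association". No other measure is attached to this check.

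The candidates are listed next: "Considered clinical variables in model building are: gender, age at diagnosis, tumour location, treatment modality, pathology, education, time since treatment". A deviance criterion does appear later, but it decides which variables remain in the clinical model: "using a forward stepwise procedure with p = 0.05 (deviance criterion) as critical p-value to stay in the model". The likelihood ratio test is reserved for nested models. Dose metrics enter afterwards, when the clinical model is "extended by a stepwise addition of dosimetric variables which are ranked in the univariable analysis"; no shape check is stated for them. Section 7.2.4 mentions no spline, fractional polynomial or other check of functional form.

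**The concern.** The step is evidently meant to detect curvature. AUC depends only on how patients are ordered by predicted risk, and the three named transformations keep that order or exactly reverse it. A criterion that sees only order cannot respond to curvature of a monotone relation.

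The stake is calibration rather than discrimination. Section 2 intends the NTCP model to estimate a risk for each individual patient, and section 7.2.4 foresees its use in comparing treatment plans. A wrong functional form can leave the AUC untouched and still bias the predicted probabilities, chiefly at the low and high ends of the predictor.

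**Working it through.** The protocol gives no figure on this point, so there is none to reproduce. The check has three parts.

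**1. The identity.** A one-predictor logistic model fits risk = 1/(1+exp(−(a + b·g(x)))), which is monotone in g(x). The AUC is the probability that a random case has a higher fitted risk than a random control, so it uses ranks only.
- If g is increasing (log, square root) and b keeps its sign, the order of patients is the same and AUC[g(x)] = AUC[x].
- If g is decreasing (inverse), b changes sign to compensate and the order is again the same.
- The AUC can differ only if the fitted direction of effect differs between forms. It then moves from A to 1 − A.

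**2. Numerical check of the identity.** Inputs from section 7.1: n = 120 ("including 120 patients will allow building a sufficiently complex prediction model combining four dosimetric and/or clinical features") and event rates of 0.2 and 0.5, used as the event-rate parameter. Assumed: a skewed positive predictor, with 1,000 datasets per scenario.

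| Effect | AUC changed: log | square root | inverse |
|---|---|---|---|
| Strong, log-shaped | 0 of 1,000 at each event rate | 0 | 0 |
| Weak | 7–9% | 4% | 13–19% |
| None | 15–17% | about 7% | 32–33% |

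Every change was a reversal of the fitted slope. In those datasets the larger AUC was at most about 0.60 (log, square root) or 0.65 (inverse), so these were predictors with little discrimination. A very skewed predictor with slope 1 per SD showed reversals in about 3–5% of datasets when the truth was linear or inverse. A non-monotone form (squared distance from the median) does change the AUC.

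One dataset with a true log shape shows the contrast. The AUC was 0.7327 for all four forms. The deviance was 146.80 untransformed, 143.81 log, 144.83 square root and 147.10 inverse. Log improves deviance by 146.80 − 143.81 = 2.99. Over the strong-effect datasets, log had lower deviance than the untransformed variable in 80–81%, with a median gain of about 2.9–3.4.

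**3. What a working criterion would gain.** All forms have the same number of parameters, so a difference in AIC equals the difference in deviance. Rule tested: use a transformation only if AIC falls by more than 2. Assumed: n = 120, event rate about 0.35, log-odds slope 1 per SD, age spread over 20–80, and a strongly right-skewed predictor for the last two rows. Entries are the root mean squared error (RMSE) of predicted risk.

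| Predictor, true form | Untransformed | Margin rule | Change |
|---|---|---|---|
| Age, log | 0.057 | 0.057 | about 0 |
| Age, inverse | 0.072 | 0.062 | −0.010 |
| Age, linear | 0.048 | 0.051 | +0.003 |
| Skewed, log | 0.086 | 0.069 | −0.017 |
| Skewed, inverse | 0.118 | 0.060 | −0.058 |

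When the truth is linear, the rule picks a transformation by chance in about 5–11% of datasets.

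**The case against.** **The criterion is inferred.** The sentence on transformations names no measure, and section 7.2.3 tests associations by Wald tests. A likelihood-based reading would work, and the gap would then be an unnamed criterion that an analysis plan could supply. It stands that the AUC is not repeated in that sentence. But section 7.2.4 gives the word one meaning, in the same paragraph, and that is the natural reading.

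**The check can sometimes fire.** A reader might infer that it can never choose a transformation, or that the AUC is equal in every dataset. The documents do not support that: slopes can reverse, and the list of transformations is open-ended. This stands, and it limits the claim to selection on merit.

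**The reach is small.** Gender, tumour location, treatment modality and pathology are categorical, and education is probably ordinal. Time since treatment hardly varies at a given visit (windows of 1 month in section 3.4, 4 weeks in section 5.1). That leaves age. This stands; the larger gains apply only if dose metrics are checked too.

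**Choosing by deviance has a cost.** Taking the lowest deviance without a margin improved age from 0.057 to 0.054 under a log truth, but worsened it from 0.049 to 0.054 under a linear truth, with a wrong switch in 44% of datasets. The loss (0.005) exceeds the gain (0.003). This stands, and is why a margin is needed. At a slope of 0.5 per SD the margin rule gives age almost nothing: 0.0565 to 0.0568 (log truth) and 0.064 to 0.062 (inverse truth).

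**Two further inferences fail.** A reader might set these errors against the rMSPE of 0.1 in section 7.1 as if that were the total permitted error. There it is a sample-size input for a four-predictor model, not an allowance for the shape of one variable. A reader might also predict that the report will claim non-linearity was excluded; nothing in the protocol says so.

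**Conclusion.** The concern holds in a limited form. Under the definition of association in section 7.2.4, the transformation check cannot select log, square root or inverse on merit. This is a rule that does not do its job, rather than a detail left for later. It follows from the rank property of the AUC; its one textual assumption is that association carries the same meaning in both sentences.

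The consequence is minor for the clinical variables as listed: for age, between a gain of 0.010 and a loss of 0.003 in RMSE at slope 1 per SD. It would matter more for skewed dose metrics (gains of 0.017 to 0.058), but the protocol does not say that they are checked. These sizes rest on the assumed slope, event rate and predictor distributions. They describe single-predictor models, not the final multivariable ones.

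**What to change.** In section 7.2.4, state three things:

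- Transformed and untransformed forms are compared by deviance/AIC, and the untransformed variable is kept unless AIC falls by a stated margin, for example 2.
- The choice is made afresh inside the cross-validation and inside the bootstrap samples used for optimism correction.
- Whether the check also applies to the dose metrics.

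The AUC stays as the measure of discrimination. The cost is a sentence or two of text, with no new data or visits; deviance is already used in the stepwise step. The statistical price is the occasional chance transformation, which the optimism correction can reflect only if the choice is repeated within each resample.
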